7 CHANGES IN CONDUCT OR PLANNED ANALYSES FROM THE PROTOCOL

There are no changes to the analyses as detailed in the protocol.

8 OVERALL STATISTICAL CONSIDERATIONS

8.1 General Conventions

The following general comments apply to all statistical analyses and data presentations:

- Summaries will include frequency and percentages for categorical data; frequency and median for ordinal data; and frequency, mean, standard deviation, and median, minimum and maximum for quantitative data.
- Duration variables will be calculated using the general formula (end date – start date) + 1.
- Change from baseline will be calculated for each subject at the specified time point as the value at the specified time point minus the baseline value.
- If the reported value of a clinical laboratory parameter cannot be used in a statistical summary table (eg, a character string is reported for a parameter of the numerical type), a coded value must be appropriately determined and used in the statistical analyses. In general, a value or lower and upper limit of normal range such as '< 10' or '≤ 5' will be treated as '10' or '5' respectively, and a value such as '> 100' will be treated as '100.' However, the actual values as reported in the database will be presented in data listings. Data will be reviewed on an ongoing basis in a blinded manner to assess the frequency of occurrence of laboratory parameters reported as a character string.
- Individual subject listings of all data represented on the eCRFs will be provided to facilitate the investigation of tabulated values and to allow for the clinical review of all efficacy and safety parameters.
- Version 9.3 (or higher) of SAS® statistical software package will be used to provide all summaries, listings, graphs, and statistical analyses.

8.2 Baseline Definition

In general, baseline is defined as the value closest to but prior to the initiation of test article administration. If no test article is received, baseline is defined as the value closest to but prior to randomization.

For pathogen determination, baseline is defined as either Day –1 or 1. For subjects with cellulitis/erysipelas, if no acceptable baseline infectious material has been obtained or if no pathogens have been identified from the baseline sample, a Day 2 or 3 microbiological sample can be used as baseline if the sample is considered acceptable. If no test article is received, for pathogen determination, study day is defined based on date of randomization.

For analyses of vital signs and ECGs, if no value is available prior to the initiation of test article administration, a value within 2 hours after initiation of test article administration can be used as baseline.

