In Phase 1 studies of iv administration, modest and reversible alanine aminotransferase (ALT) increases were seen, most notably with iv doses of 300 mg or greater. Transient increases in heart rate (HR) were observed following administration of single and multiple doses of omadacycline, with a dose dependent mean increase of up to 15 to 20 beats per minute (bpm) compared to placebo. The increases in HR were rarely reported as adverse events (AEs) and not associated with any other cardiac findings. These increases were most evident within the 6 hours post-infusion. Following po administration, an increased incidence of gastrointestinal (GI) AEs, particularly nausea, was noted in early studies, which were most notable at po doses of 400 mg or greater. Of note, different po formulations evaluated in early studies (eg, capsule versus tablet) may have influenced the GI safety profile. In Phase 1 studies there were no discontinuations due to drug-related AEs in any subject who received multiple doses of omadacycline.

In the Phase 2 cSSSI study, the most frequently reported AEs were GI related occurring in 19% of omadacycline treated and 17% of linezolid-treated subjects. Nausea and vomiting were reported in 10% and 5%, respectively, of omadacycline-treated subjects primarily during po treatment, compared to 7 and 4%, respectively, of linezolid-treated subjects. Premature discontinuation of treatment due to an AE was very infrequent, occurring in 0.9% of omadacycline subjects and 1.9% of linezolid subjects. There was no pattern of adverse changes in laboratory safety parameters among subjects treated with omadacycline or linezolid. In particular, there was no clinical or statistical difference between the treatment groups in ALT values or in other liver enzymes.

An increase in mean HR was observed, but to a lesser extent than what was observed in Phase 1 studies. This effect was transient and no QT prolongation was observed, consistent with the negative findings from testing of omadacycline in a dedicated corrected QT interval (QTc) study. Three subjects treated with omadacycline had AEs of tachycardia; 1 other subject reported palpitations. All 4 of these AEs were mild in intensity, all were assessed as either unrelated or unlikely related to test article, and none resulted in discontinuation of study treatment.

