16.1.1 Vital Signs

Vital signs include BP, pulse/heart rate, body temperature, and respiratory rate. Vital signs should be recorded at all visits, with the exception of the Final Follow-up assessment (see [Section 8](#)).

- In addition, blood pressure and pulse rate should be measured within 30 min before, and approximately (\pm 15 minutes) 1 hour after and 3 hours after the completion of the first dose on Day 1
- Blood pressure and pulse rate should be measured within 30 min before, and approximately (\pm 15 minutes) 1 hour after and 3 hours after the completion of the odd numbered dose on Day 2
- Blood pressure and pulse rate should be measured within 30 min before, and approximately (\pm 15 minutes) 1 hour after and 3 hours after the completion of the odd numbered dose on Day 3

In the event that the subject takes the dose before arriving for the Day 2 or Day 3 office visit, the site should collect the 1 and 3 hour post dose measurements if possible, if not then a single measurement should be made at any time during the visit and the date and time recorded.

The subject's vital signs should be captured after at least 5 minutes of rest while in a non-standing position (supine or semi-recumbent, head of bed from 0° to 90°). Subsequent vital sign measurements should be captured in the same non-standing position.

Systolic and diastolic blood pressure will be measured using an automated validated device, with an appropriately sized cuff.

Pulse will be measured using an automated validated device, when available. If not available, pulse will be measured manually.

In addition to the above, BP and heart rate may be measured whenever clinically indicated at the discretion of the treating physician. Any subject who experiences an AE of cardiac chest pain, palpitations, or tachyarrhythmia while on study should have an ECG and an evaluation by the investigator (see [Section 16.1.3.1](#)).

Temperature will be obtained using an electronic (rapid reading) device whenever possible. Respiratory rate will be determined by observation.

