11.2 Vital Signs

Blood pressure (systolic and diastolic), respiratory rate and pulse/heart rate will be summarized using descriptive statistics at the following time points: baseline, Day 1, Day 2, Day 3, Day 7, Day 10, the EOT visit and PTE visit, but not the final Follow-up Visit. Pulse rate and blood pressure will be summarized for the following additional time points: a) 30 minutes before, 1 hour after and 3 hours after the completion of the first dose on Day 1, and b) 30 minutes before and 1 hour after and 3 hours after the completion of the odd numbered doses on Days 2 and 3. In the event the subject takes the dose before arriving at the office visit, the site should collect the 1 and 3 hour post dose measurements, if possible. If not then a single measurement at any time during the visit should be obtained.

Descriptive statistics of the change from baseline to each post-baseline time point will also be provided. Baseline is defined as the value closest to but prior to the initiation of test article administration. If no value is available prior to the initiation of test article administration, a value within 2 hours after initiation of test article administration can be used as baseline. The change from baseline to the minimum and maximum post-baseline values (including any unscheduled post-baseline assessments) will also be summarized by treatment group.

Figures (line graphs) of value and change from baseline for systolic and diastolic blood pressure, and heart rate by time point will also be provided by treatment group.

Post-baseline vital signs will be defined as clinically notable (CN) if they meet 1) the criterion value or 2) meet both the criterion value and the change from baseline criterion listed in Table 8. The incidence of CN vital signs will be summarized by time point and treatment group, and will be listed and flagged in by-subject listings. The overall post-baseline incidence of CN values for each vital sign parameter, which includes values from unscheduled post-baseline visits, will also be summarized. A listing will also be provided of subjects with a CN vital sign and will list all values for a vital sign noted as CN.

Table 8. Criteria for Treatment Emergent Clinically Notable Vital Signs

Vital Sign Parameter	Flag	Criterion Value	Change from Baseline
Systolic Blood Pressure (mmHg)	High (CH)	≥ 180	Increase of ≥ 20 mmHg
	Low (CL)	≤ 90	Decrease of ≥ 20 mmHg
Diastolic Blood Pressure (mmHg)	High (CH)	≥ 105	Increase of ≥ 15 mmHg

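### For a subject with no pre-dose reading, the SAP lets a vital sign or ECG taken up to 2 hours after the first dose stand as baseline, which can hide part of an early heart-rate rise

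*SAP*

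**What the plan says.** The general rule in SAP 8.2 is pre-dose: "In general, baseline is defined as the value closest to but prior to the initiation of test article administration". An exception follows. "For analyses of vital signs and ECGs, if no value is available prior to the initiation of test article administration", then "a value within 2 hours after initiation of test article administration can be used as baseline". SAP 11.2 (vital signs) and 11.3 (ECG) restate the same conditional rule.

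The protocol schedules readings on both sides of Dose 1. Section 16.1.1 states: "Vital signs should be recorded at all visits, with the exception of the Final Follow-up assessment", which includes Screening. It continues: "In addition, blood pressure and pulse rate should be measured within 30 min before" and, with a tolerance of 15 minutes, about "1 hour after and 3 hours after the completion of the first dose on Day 1". Under Protocol 16.1.3.1 the ECG is taken at Screening and at EOT, and otherwise after certain cardiac adverse events or on clinical indication.

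Protocol 9.1 describes a transient, dose-dependent rise in heart rate with omadacycline, with a mean of up to 15 to 20 bpm over placebo in Phase 1. On timing it says: "These increases were most evident within the 6 hours post-infusion". The rise was smaller in the Phase 2 patient study, and no QT prolongation was seen.

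**The concern.** A baseline is meant to describe the untreated subject. Dose 1 contains active drug in both arms (450 mg omadacycline or 600 mg linezolid), so a reading taken after it is an on-treatment value. If that reading becomes the baseline, any effect already present is subtracted from every later change for that subject.

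Heart rate is the cardiovascular effect that the protocol itself reports for omadacycline, and the documents state no such effect for linezolid. Any understatement would therefore fall mainly on the omadacycline arm and make its increase look smaller.

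For the ECG, no routine recording falls in the 2-hour window. An ECG found there is either a late Screening ECG or one taken on clinical indication, possibly because of a cardiac event. The second kind is a poor choice of baseline.

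**Working it through.** The plan gives no figure on this point to reproduce. The check has three steps.

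**1. Which scheduled reading can the fallback pick up?** The 1-hour reading has a tolerance of 15 minutes, so it falls 60 − 15 = 45 to 60 + 15 = 75 minutes after Dose 1, inside the 120-minute allowance. The 3-hour reading falls at 180 − 15 = 165 to 180 + 15 = 195 minutes, outside it. The 1-hour pulse and blood pressure are therefore the scheduled values that the rule would use.

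**2. What happens to that subject's changes?** Let B be the untreated heart rate and e the drug effect in the substituted reading. The recorded baseline is B + e.

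- Change at 1 hour: (B + e) − (B + e) = 0, whatever e is. SAP 11.2 summarises the 1-hour reading as a post-dose time point and does not say that it leaves that summary when it serves as baseline.
- Change at a later time with value Y: Y − (B + e), which is e lower than the true change Y − B.

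On the Phase 1 mean figure, e is at most about 15 to 20 bpm. Its value 45 to 75 minutes after a 450 mg oral dose is not given.

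**3. What is the effect on the arm mean?** If a share f of omadacycline subjects uses the fallback, the mean change is understated by f × e. Neither input is stated for this trial. I assume f from 0.5% to 10% and e from 5 to 20 bpm; the upper end of e is the Phase 1 maximum mean. For scale, 704 / 2 = 352 subjects per arm.

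| f (assumed) | Subjects of 352 | e = 5 bpm | e = 15 bpm | e = 20 bpm |
|---|---|---|---|---|
| 0.5% | 1.8 | 0.025 | 0.075 | 0.10 |
| 1% | 3.5 | 0.05 | 0.15 | 0.20 |
| 5% | 17.6 | 0.25 | 0.75 | 1.0 |
| 10% | 35.2 | 0.5 | 1.5 | 2.0 |

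In reverse, a 1 bpm understatement needs f = 1/20 = 5% (18 subjects) at e = 20, or f = 1/15 = 6.7% (24 subjects) at e = 15. With strictly pre-dose baselines this bias is zero.

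**Comparison with the plan's other conventions.** The laboratory baseline in SAP 11.4 falls back from central to local values but always stays before the first dose. Protocol 22.7.2 and 22.7.3 describe change from Screening for vital signs and ECGs, which is an untreated reference. SAP section 7 declares no changes from the protocol's analyses, so the post-dose fallback is not disclosed as one.

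**The case against.** The strongest reply is that the rule should rarely operate. Blood pressure and pulse are scheduled twice before dosing, at Screening and within 30 minutes before Dose 1, and both must be missing. The ECG is required at Screening. Protocol 14.3.1.1 places Dose 1 after the required Screening procedures. The rule is also prespecified and uses an observed value, so it does not breach the SAP 8.3 provision against imputing missing data. All of this stands, and it is why the point is minor. It does not make the change score right for the subjects whom the rule reaches.

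A reader might infer more than the documents support:

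- **That post-dose baselines are generally allowed.** They are not; the condition is that no earlier value exists.
- **That clinically notable flags are lost.** Under SAP 11.2 a value can be flagged on the absolute criterion alone, so a heart rate of 120 bpm or more is flagged whatever the baseline. Only a separate count of values that also meet the change criterion could move.
- **That a QTc effect is hidden.** Protocol 9.1 reports no QT prolongation and a negative dedicated QTc study, and no ECG is scheduled in the window.
- **That the full 15 to 20 bpm applies here.** That is the top of a dose-dependent Phase 1 range. The 6-hour timing refers to infusion, and the Phase 2 effect was smaller.
- **That the 1-hour reading was scheduled to detect this effect.** The protocol gives no such purpose; section 16.1.4 calls the safety assessments standard for the indication.

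Observed values at 1 and 3 hours are also summarised in their own right, so a rise would remain visible there.

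**Conclusion.** The concern holds as a minor, conditional point. The fallback gives a change score that does not measure change from an untreated state. For an affected omadacycline subject, that score is too low by whatever heart-rate effect was present at the substituted reading.

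At arm level the understatement is about 0.2 bpm or less if 1% of subjects are affected. It reaches 1.5 to 2.0 bpm only if 10% are affected and the full Phase 1 mean effect applies. Both the share and the effect are assumptions; the documents give neither for this trial. For ECGs the issue is limited to the possible use of a late or clinically prompted recording as baseline. Efficacy analyses and sample size are untouched.

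**What to change.** Delete the post-dose fallback from SAP 8.2, 11.2 and 11.3, and define baseline for vital signs and ECGs as the last value before the first dose, whether from Screening or Day 1. For subjects with no such value:

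- show the observed post-dose values;
- leave the subject out of the change-from-baseline and QTcF-increase summaries;
- report the number of such subjects by arm.

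The cost is wording in three places. The downside is that a few subjects drop out of the change tables.

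If the sponsor prefers to keep the fallback, the minimum is to list it in SAP section 7, report how many subjects use it in each arm, and repeat the change summaries without them.

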8.3 Handling of Missing Data

Missing data will be handled as outlined below:

- All missing and partial dates for adverse events or for medications received after randomization will be queried for a value. If no value can be obtained, substitutions will be made as detailed in [Appendix 3](#). These substitutions will be used in calculations; however, the actual value recorded on the eCRF will be used in all listings.
- Missing start and stop times for prior and concomitant antibiotics will be queried for a value. If no value can be obtained but the site indicates the antibiotic was received (onset time) prior to the first dose of test article, 00:01 will be used for the onset time. If the site also indicates that the end time was prior to the first dose of test article, 00:01 will be used for end time. The actual value (blank) will be recorded on the eCRF and will be used in the listings.
- Missing times for lesion measurements will be queried for a value. If minutes are not available, the time will be recorded to the closest hour.
- If the time of the outpatient dose of test article on Day 1 is missing, it will be imputed to 23:59.
- If no value can be obtained for all other times for events and assessments occurring after randomization, the time will not be imputed but will remain missing.
- The severity and causality assessment for adverse events cannot be missing. Missing data will be queried for a value.

For clinical and microbiological response, missing data will be handled as follows:

- For the primary outcome measure (Early Clinical Response at 48 to 72 hours):
 - The subject will be considered to have missing data if there is no lesion size measurement (either length or width) at either baseline or 46 to 72 hours after the first dose of test article. Subjects with missing data will be defined as an Indeterminate response which is essentially a Clinical Failure for the primary analysis (mITT and ITT populations).
 - If the time of administration of the first dose of test article is missing, the subject will be defined as an Indeterminate response which is essentially a Clinical Failure for the primary analysis (mITT and ITT populations).
- For the secondary outcome measures (investigator's assessment of Clinical Response at the EOT and PTE Visits):
 - Subjects will be defined as an Indeterminate if the investigator cannot determine whether the subject is a Clinical Success or Failure at the EOT or PTE Visits or the subject has a missing response. By definition, subjects with an Indeterminate response are included in the denominator for analyses in the mITT and micro-mITT populations, and thus, are considered Clinical Failures. Subjects with an Indeterminate response are excluded from the CE-EOT, CE-PTE, ME-EOT and ME-PTE populations.

- For microbiologic response:
 - If no source specimen is obtained and the subject has an investigator's assessment of Clinical Response, the per-pathogen microbiological response is based on the investigator's assessment of Clinical Response (ie, the response is a presumed response). A per-pathogen microbiological response at the EOT Visit or PTE Visit will be considered Indeterminate only if the Clinical Response at EOT or PTE is also Indeterminate.
- Missing values for other individual data points will remain as missing. Missing values will not be imputed and only observed values will be used in data analyses and presentations.
- Where individual data points are missing, categorical data will be summarized based on reduced denominators (ie, only subjects with available data will be included in the denominators).

8.4 Interim Analysis

An interim analysis to assess efficacy or safety is not planned.

8.5 Pooling Strategy for Study Sites

Data will be pooled across sites for all efficacy and safety analyses. An analysis of the primary (Early Clinical Response) and secondary (Investigator assessment of clinical response) efficacy outcomes will be conducted by site. Sites that enroll less than 10 subjects per arm will be pooled together for the by site analysis.

8.6 Visit Windows/Unscheduled Visits

For the primary efficacy outcome, if more than one assessment of the lesion size is done in the 46-72 hour window, the latest will be used. For secondary and additional efficacy outcomes, the data collected at the EOT and PTE Visits, regardless of when these occur will be utilized in the analysis in the mITT population. The CE and ME populations exclude subjects with a visit occurring outside the window allowed per protocol.

For each safety outcome, analyses will utilize assessments occurring during the scheduled visit windows (provided in [Table 7](#)). Thus, if a subject has a visit outside the scheduled visit window, for example, a PTE Visit occurred 20 days after the subject's last day of therapy, the assessment will not be summarized with the PTE Visit but will be considered an unscheduled assessment. If a subject does not have an assessment at a scheduled visit and an unscheduled assessment was taken within the window for the time point (for example, 7 to 14 days after the subject's last day of therapy for PTE), these assessments will be summarized in the by time point analyses. If more than one measurement is taken during the visit window, the value taken on the scheduled visit will be utilized or if no scheduled visit was done, the first (earliest) measurement in the visit window will be used. If more than one measurement is taken on the same day, the assessment closest to the start of the dose will be used for on treatment values and the last measurement on the day will be used for post-treatment values. For worst overall post-baseline analyses, all assessments including those obtained from unscheduled visits will be included.

Table 7. Scheduled Study Visits

Study Visit	Study Day	Notes
Baseline	Day -1 or Day 1	Except where indicated, last measurement prior to the first dose of test article. Screening assessments are to be taken within 24 hours prior to the first dose of test article. If no test article is taken, the date and time of randomization is used in place of the first dose of test article.
On Treatment (note: analysis visit will be each Study Day)	Day 1, Day 2, Day 3, Day 7, Day 10	The Day 3 visit is to occur within 46 to 72 hours after the first dose of study drug and thus, may occur on Study Day 4. A Day 10 visit is will be conducted for subjects with treatment extending beyond 9 days, unless this visit coincides with the EOT Visit.
EOT		Within 2 days following the last dose of test article
PTE		7 to 14 days after the subject's last day of therapy
Final Follow-up (FU)	Day 30 to 37	30 to 37 days after the start of the first dose of test article

Study Day is calculated relative to the first dose of test article (Day 1); there is no Day 0 – the day prior to the first dose of test article is Day -1. If no test article is taken, study day is calculated relative to the date of randomization.

